4.1. Sample Size

A two group continuity corrected Chi-square test with a 0.05 two-sided significance level will have 89% power to detect the difference between a Sham group recurrence free rate of 0.600 and a FAI treated group recurrence free rate of 0.880 (odds ratio of 0.205) when the sample sizes are 40 and 80, respectively (a total sample size of 120).

4.2. Randomization, Stratification, and Masking

Subjects will be randomly assigned in a 2:1 ratio to either the FAI insert or sham injection through a central Interactive Voice Response System (IVRS). A blocked randomization will be used and randomization will be stratified on the basis of systemic treatment to control uveitis at the time of study entry. The three strata are: Not receiving systemic treatment, Receiving systemic treatment – corticosteroid therapy, and Receiving systemic treatment – immunosuppressive therapy. Stratification will be achieved dynamically through the IVRS.

To minimize bias, two investigators will be used at each study site. The unmasked treating investigator will inject the FAI insert or perform a sham injection and perform all assessments on study Day 1. The second investigator will serve as the masked assessing investigator and will perform all study assessments after Day 1. Only the unmasked treating investigator will know the assigned study treatment. Study personnel will use every reasonable effort to maintain the study mask.

Unmasking a subject's treatment to the assessing investigator should only be done in emergency situations for reasons of subject safety. In the event that an emergency unmasking is required, the assessing investigator/medically qualified designee has the authority to unmask a subject's treatment using IVRS, or its backup system if IVRS is not functioning. If possible, the assessing investigator/medically qualified designee should contact the PPD medical monitor or designee

before breaking the mask. When the masked treatment code is broken, the date and time of unmasking, name of person doing the unmasking, and the reason for unmasking must be fully documented in the source documentation. Treatment unmasking will also be recorded on the eCRF, including whether the FAI insert was removed and if so, the removal date. In the rare event that the FAI insert is removed, the subject should continue to be followed for safety and recurrence of uveitis through Month 36.

Randomization and unmasking data, for those subjects who were unmasked during the study, will be presented in a listing.

4.2.1. Masking of Study Team

Prior to the Month 6 database lock, study team members at PPD and pSivida Corp. will be masked to the treatment assignments, with the exception of the PPD randomization team. After the Month 6 database lock, the PPD Biostatistics, Programming and Medical Writing team members and pSivida will become unmasked. The PPD Clinical and Data Management team members will remain masked to subject-level treatment assignments until after the Month 36 database lock.

4.3. Analysis Population

4.3.1. Intent-to-Treat (ITT)

The ITT population will include all randomized subjects. The ITT population will be used for the primary efficacy analysis and all efficacy endpoints.

All subjects in the ITT population will be analyzed according to the treatment they were randomized to receive and not according to what they actually received, in the event there is a discrepancy. Similarly, in any ITT analysis by systemic treatment at study entry (randomization stratification factor), subjects will be analyzed by the strata to which they were randomized, not the actual strata, in the event there is a discrepancy.

4.3.2. Per Protocol (PP)

Analysis on the PP population will be used as a supplement to the ITT analysis and will be performed for all efficacy endpoints. The PP population will be defined separately for the Month 6, Month 12 and Month 36 analyses and will exclude all subjects in the ITT population who meet any of the following criteria:

- Received systemic treatment for recurrence of uveitis in fellow eye
- Received an imputed endpoint at the 6 month (or the 12 month or the 36 month) endpoint of the study
- Failed screening, without exemption, but received FAI insert
- Had a major protocol deviation

Protocol deviations, both major and minor, will be identified prior to database lock and study unmasking at Month 6 and prior to database locks at Months 12 and 36. The review and identification of protocol deviations at Months 12 and 36 will be conducted in an unmasked manner since pSivida and the PPD biostatistics team are unmasked at the Month 6 database lock.

All subjects who failed screening but received FAI insert will be determined at Month 6 database lock.

Additional sensitivity analyses involving alternative definitions of the PP population may be conducted, if warranted.

All subjects in the PP population will be analyzed according to the treatment actually received and not according to the treatment they were randomized to receive, in the event there is a discrepancy. Similarly, in any PP analysis by systemic treatment at study entry (randomization stratification factor), subjects will be analyzed by the actual strata to which they belong and not according to the strata under which they were randomized, in the event there is a discrepancy.

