A two group continuity corrected Chi-square test with a 0.05 two-sided significance level will have 89% power to detect the difference between a Sham group recurrence free rate of 0.600 and a FAI treated group recurrence free rate of 0.880 (odds ratio of 0.205) when the sample sizes are 40 and 80, respectively (a total sample size of 120).

Study Populations:

The ITT (Intent to Treat) population will include all subjects randomized into the study; analyzed as randomized. The safety population will include all subjects randomized into the study; analyzed as treated. The per protocol (PP) population will be defined separately for the month 6, month 12 and month 36 analyses and will exclude all subjects in the ITT population who meet any of the following criteria:

- Received systemic treatment for recurrence of uveitis in fellow eye
- Received an imputed endpoint at the 6 month (or 12 month or 36 month) endpoint of the study
- Failed screening, without exemption but received FAI insert
- Had a major protocol deviation

Efficacy Analyses:

Efficacy analyses will be performed on both the ITT population and the PP population at 6, 12 and 36 months. The primary efficacy analysis will be performed on the ITT population at 6 months and will be the difference between study groups in the proportion of subjects who have a recurrence of uveitis. The primary efficacy analysis will be conducted after all subjects in the study have completed 6 months of treatment or have discontinued. A continuity corrected Chi-square analysis will be used to assess the statistical significance of a difference between study groups in the primary efficacy analysis.

Recurrence will be imputed in the following circumstances:

- A subject who has not previously experienced a recurrence and does not complete the required eye examinations at Month 6 (or Month 12 or 36 for the Month 12 or 36 analyses, respectively) for any reason will be considered as having a recurrence.
- A subject who has not previously experienced a recurrence and takes a prohibited systemic concomitant medication or a prohibited local concomitant medication in the study eye at any time during the study prior to Month 6 (or Month 12 or 36 for the Month 12 or 36 analyses, respectively) will be considered as having a recurrence.

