9.17. Subject Withdrawal Criteria

Subjects have the right to withdraw from the study at any time, for any reason, without jeopardizing their medical care. The following are examples of criteria for considering withdrawal from this study:

- Withdrawal of subject consent; or
- Intercurrent illness including death that prevents continuation of regular follow-up visits

All subjects will be followed for safety through their final visit unless withdrawn from the study for the above reasons.

The investigator, IRB/EC and pSivida Corp. also have the right to withdraw subjects from the study for the following reasons: when continuation may jeopardize the health of the subject, protocol violations, AEs or concurrent conditions, administrative or other reasons.

Subjects who withdraw for any reason from the study following randomization and administration of study treatment (FAI insert or sham injection) will not be replaced. All randomized subjects will be followed for as long as they agree to return for visits.

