5.2. Protocol Deviations

The investigator is not to deviate from the requirements from this protocol without prior approval from pSivida Corp. unless necessitated by a medical emergency (i.e., those that impact subject safety or the validity of the study). Any deviation from the protocol, with or without prior pSivida approval, will be recorded including the following information:

- Investigator site
- Subject
- Subject visit
- Description (including associated Significant Protocol Deviation rule number, if applicable)

- Date of occurrence
- Ethics Committee notification date if known
- Significant (Yes/No)

Significant protocol deviations will be defined in the Significant Protocol Deviations Rules document. Each significant deviation will be assigned a rule number. As the study is ongoing, additional significant protocol deviations can also be spontaneously identified or defined during trending and review of protocol deviations by pSivida and/or the project team during the regularly planned study deviation review meetings and the significant Protocol Deviations Rules document will be updated.

All protocol deviations will be reviewed and assessed as to significance prior to each database lock. The list of protocol deviations (significant or minor) that are additionally considered major for the purposes of analysis (i.e. result in exclusion from the PP population) will also be identified prior to each database lock.

6. Demographics and Baseline Characteristics

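### The per-protocol rule removes unexempted screening failures automatically only if they received the FAI insert, so the supportive PP comparison can be asymmetric by arm

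*SAP*

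**What the plan says.** SAP 4.3.2 builds the PP set separately for Months 6, 12 and 36 by removing ITT subjects who meet any of four criteria. One is "Failed screening, without exemption, but received FAI insert". Protocol 14.2.3 has the same criterion, and the protocol synopsis reads "Failed screening, without exemption but received FAI insert". SAP 4.3.2 then fixes the timing, with the same limit: "All subjects who failed screening but received FAI insert will be determined at Month 6 database lock". There is no matching sentence for sham.

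The other three criteria apply in either arm: systemic treatment for a fellow-eye recurrence, an imputed endpoint ("Received an imputed endpoint at the 6 month (or the 12 month or the 36 month) endpoint of the study"), and a major protocol deviation. On deviations, SAP 5.2 says "Significant protocol deviations will be defined in the Significant Protocol Deviations Rules document". It adds that "The list of protocol deviations (significant or minor) that are additionally considered major for the purposes of analysis" is to be settled before each database lock. Neither the rules document nor the list is reproduced in the protocol or SAP.

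SAP 4.3.2 also leaves a door open: "Additional sensitivity analyses involving alternative definitions of the PP population may be conducted, if warranted".

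SAP section 8 makes PP supportive of ITT. SAP 8.1.1 nevertheless applies the primary test to study-eye recurrence in PP at Months 6, 12 and 36.

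**The concern.** A PP set is useful as a check on ITT only if subjects leave it for the same reasons in both arms. Here an ineligible subject without an exemption leaves automatically after receiving the insert. An equally ineligible sham subject leaves on that ground only through a classification that the documents do not fix. The PP treatment difference could then move because of the exclusion rule alone, and either a gap or an agreement between PP and ITT would be harder to read.

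The plan expects such cases: SAP 6.4 provides for recording and listing unmet entry criteria and sponsor waivers, without restriction by arm. At Months 12 and 36, SAP 4.3.2 has deviations reviewed with treatment known. The PP status of an ineligible sham subject could therefore turn on an unmasked judgement, where an FAI subject's follows from a rule.

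**Working it through.** **The plan's own figure.** Inputs from SAP 4.1 and protocol 14.1: recurrence-free rates 0.600 (sham) and 0.880 (FAI), 40 and 80 subjects, two-sided 0.05, continuity-corrected chi-square, stated power 89%. The odds ratio is (0.600/0.400)/(0.880/0.120) = 0.2045, matching 0.205. Inverting the continuity correction gives an effective sham size of 40 x [1 - 1.5/(2 x 40 x 0.28)]^2 = 34.82. With 2:1 allocation the power is then 89.2%, so the stated figure is reproduced. Nothing in this point changes it.

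**Routes out of PP for an ineligible subject without an exemption.**

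| Route | FAI | Sham |
|---|---|---|
| Screening-failure criterion | automatic | not named |
| Major deviation | if so classed | if so classed |
| Imputed endpoint, or systemic treatment for a fellow-eye recurrence | possible, unrelated to eligibility | possible, unrelated to eligibility |

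On the ground of ineligibility, the sham column has only the second row.

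**Size of the shift.** Let f be the share of the PP sham set kept only because of this rule, k the recurrence-free rate of those kept, r the rate of the other PP sham subjects, and d = r - k. With them the sham rate is (1 - f)r + fk; without them it is r. The FAI arm is the same under both rules and cancels. The shift in the FAI-minus-sham difference is therefore

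r - [(1 - f)r + fk] = f(r - k) = f x d.

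The documents give no ineligibility rate and no outcome for ineligible subjects, so f and d are assumptions. Results in percentage points:

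| f | d = -0.10 | d = 0 | d = +0.30 |
|---|---|---|---|
| 2.5% | -0.25 | 0 | +0.75 |
| 5% | -0.5 | 0 | +1.5 |
| 10% | -1.0 | 0 | +3.0 |

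Of 40 sham subjects, 2.5% to 10% is 1 to 4.

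**Cross-check from the planning rates.** Hold each arm's overall rate at its planned value and let a share f of each arm be ineligible, with a rate lower than the arm's overall rate by g. The remaining subjects then have rate p + fg/(1 - f). Dropping the ineligible from both arms leaves the difference at 0.280. Dropping them from FAI only raises it by fg/(1 - f): 0.2 points at f = 2%, g = 0.10, and 3.3 points at f = 10%, g = 0.30. This is the same formula with d = g/(1 - f). If the ineligible do better, the sign reverses.

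**One subject.** Take the planned sham result, 24/40 = 0.600, with one kept ineligible subject.

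- If that subject recurred, the set without them is 24/39 = 0.615, so keeping them adds 1.5 points to the FAI advantage.
- If that subject was recurrence-free, it is 23/39 = 0.590, so keeping them takes off 1.0 point.

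A single subject's outcome is 0 or 1, so d here is +0.62 or -0.41, outside the range in the table. This is an illustration in whole subjects and does not support that range.

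**The case against.** The strongest reply is that the major-deviation criterion already covers both arms. Deviations are recorded and assessed before each lock, and at Month 6 they are identified before unmasking, so that step cannot be steered by arm. If the rules document or the lock-time list makes unexempted ineligibility major, the asymmetry disappears. That is possible, but the plan does not secure it. It would also make the FAI-only criterion redundant, and the Month 12 and 36 reviews are unmasked.

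A second reply is that the wording is a slip. A reader might infer a deliberate difference between arms, because protocol 9.17 names both where both are meant: "administration of study treatment (FAI insert or sham injection) will not be replaced". The documents do not support that inference. Protocol 14.3.5 describes a table of events related to FAI treatment that is to be given for each treatment group, so the drafters also used FAI loosely for study treatment. A slip is plausible, but it still has to be corrected, because the literal rule is the one that will be applied.

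Third, a major deviation is not the only way any sham screening failure can leave PP; the imputed-endpoint and fellow-eye criteria can remove one too. That is right. The point concerns removal for ineligibility.

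Fourth, eligibility is checked at screening and again on Day 1 before assignment, and exempted subjects fall outside the criterion in both arms. So f = 10% may be generous. This stands.

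**Conclusion.** The point holds as a gap in a stated rule: as written, ineligibility without exemption removes FAI subjects from PP automatically and does not do so for sham subjects. Whether any asymmetry arises depends on the deviation rules and lock-time lists, which are outside the protocol and SAP.

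Size and direction are unknown. The -1.0 to +3.0 points rest entirely on the assumed f and d. The one-subject figures, -1.0 or +1.5 points, rest on the planned 24/40.

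A reader might infer that the rule favours FAI. The documents do not fix the sign: some entry failures may carry a higher recurrence risk and others, such as too few prior recurrences, a lower one. Larger shifts can be produced by also assuming that many sham recurrences were imputed and so left PP, but the documents give no such count.

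Nor does the point reach the primary result. The ITT analysis, alpha and sample size are unaffected, and PP is supportive. It is still worth correcting, because PP carries an inferential test at three time points and the sham arm is small.

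**What to change.** In SAP 4.3.2, in both the criterion and the sentence on the Month 6 determination, change receipt of the FAI insert to receipt of study treatment, whether FAI insert or sham injection. Alternatively, state that any eligibility failure without an exemption is a major deviation in either arm.

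SAP 11.2 already records changes made after unmasking, so log this one there as such. Keep the prespecified Month 6 PP result. Beside it add an arm-neutral Month 6 PP table, labelled post hoc, under the existing clause on alternative PP definitions. Use the arm-neutral rule at Months 12 and 36. Check the rest-of-world SAP mentioned in SAP 13.3 for the same wording. Align protocol 14.2.3 and the synopsis at a next amendment; under protocol 9.15, significant protocol changes need ethics and regulatory approval, and this one can wait.

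The cost is two wording edits, one log entry and one extra table, with a possible matching edit to the rest-of-world SAP. No new data are needed, since unmet criteria and waivers are already recorded (SAP 6.4). The downside is that a few sham subjects may leave PP, and the Month 6 arm-neutral version is post hoc.

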8.1.2. Data Imputation

Data for the primary outcome only (recurrence of uveitis) will be imputed using a straightforward method:

- A subject who has not previously experienced a recurrence and does not have the required eye examination data for assessing recurrence at Month 6 (or Month 12 or Month 36 for the Month 12 or 36 analyses, respectively) for any reason will be considered as having a recurrence. If one or more of the required eye examinations, including BCVA and vitreous haze, is not completed at Month 6 (or Month 12 or Month 36), the subject will be considered as having a recurrence. Reasons for missing recurrence data at Month 6 (or 12 or 36) include, but are not limited to: discontinuation from the study prior to visit, visit occurred outside of the visit window, and missed visit.
- A subject who has not previously experienced a recurrence and takes a prohibited systemic concomitant medication as defined in Section 9.10.2 of the protocol any time during the study prior to Month 6 (or Month 12 or Month 36 for the Month 12 or 36 analyses, respectively) will be considered as having a recurrence.
- A subject who has not previously experienced a recurrence and takes a prohibited local concomitant medication in the study eye as defined in Section 9.10.2 of the protocol any time during the study prior to Month 6 (or Month 12 or Month 36 for the Month 12 or 36 analyses, respectively) will be considered as having a recurrence.

Systemic medications administered as part of a gradual dose reduction (tapering) (as described in Section 9.10.1 of the protocol) will not be considered prohibited medications for the analysis of the primary endpoint. For the analysis of the primary endpoint for US/FDA, topical steroids will not be considered a prohibited medication.

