The prohibited medication data (based on preferred terms and/or ATC codes) will be reviewed and medications will be categorized as either having a potential impact on the efficacy assessments (consistent with the US/FDA definition of the primary endpoint) or no impact on the efficacy assessments. Only prohibited medications determined to have a potential impact on efficacy assessments will be taken into consideration for data imputation. The list of prohibited medications which will result in an imputed recurrence of uveitis value, for either eye, will be identified prior to each database lock. Note: although local medications are permitted in the fellow eye, in order to ensure consistency in analysis between the study eye and fellow eye, the same list of medications prohibited in the study eye, including local medications, will be considered “prohibited” for the fellow eye for the purposes of recurrence imputation.

A listing of subjects with missing recurrence information at Month 6 (or Month 12 or Month 36 for the Month 12 or 36 analyses, respectively) will be provided. All available recurrence data for these subjects will be included in the listing.

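### Protocol deviations for the Month 12 and 36 per-protocol sets are classified unmasked although masked CRO staff remain available, and the drug list that imputes recurrence has no masking condition after Month 6

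*SAP*

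**What the plan says.** **Deviations.** For Month 6, SAP 4.3.2 puts the review before the mask is lifted: "Protocol deviations, both major and minor, will be identified prior to database lock and study unmasking at Month 6". For the later analyses it says the opposite: "The review and identification of protocol deviations at Months 12 and 36 will be conducted in an unmasked manner". The reason given is that the sponsor and the CRO biostatistics team are unmasked at the Month 6 lock. SAP 5.2 adds that the deviations "additionally considered major for the purposes of analysis (i.e. result in exclusion from the PP population) will also be identified" before each database lock. They may come from those graded significant or minor. The same section provides a document of numbered rules for significant deviations, and lets the sponsor or project team define further ones while the study runs.

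**Who is masked.** Under SAP 4.2.1 the sponsor and the CRO's Biostatistics, Programming and Medical Writing teams are unmasked after the Month 6 lock. The CRO's Clinical and Data Management teams stay masked to subject-level treatment until after the Month 36 lock.

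**Drug list.** SAP 8.1.2 says "The prohibited medication data (based on preferred terms and/or ATC codes) will be reviewed" and sorted by possible effect on the efficacy assessments. "Only prohibited medications determined to have a potential impact on efficacy assessments will be taken into consideration for data imputation". The drugs "which will result in an imputed recurrence of uveitis value, for either eye, will be identified prior to each database lock". No reviewer is named, and no masking condition is given for the later locks.

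**Status of the later tests.** SAP 8.1.1 repeats the continuity-corrected chi-square test at Months 12 and 36 in both the ITT and PP populations. It calls these analyses exploratory and supportive, without type I error adjustment.

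**The concern.** A decision on whether a deviation is major, or whether a drug counts as affecting efficacy, is a judgement that can change an analysis result. Such judgements are normally made before the people making them can see treatment arm and outcome together. At Months 12 and 36 the plan gives up that protection for deviations, on the ground that the sponsor and the statisticians are already unmasked, while other staff at the CRO are kept masked.

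The drug list could matter more if it were handled in the same way, because it acts on the ITT outcome. "A subject who has not previously experienced a recurrence and takes a prohibited systemic concomitant medication" before the time point is counted as a recurrence. Under the imputed-endpoint criterion of SAP 4.3.2, that subject then also leaves the PP set.

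At stake is the credibility of the plan's between-arm recurrence tests beyond Month 6, for an insert described as releasing drug for 36 months.

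**Working it through.** **1. The plan's own figure.** SAP 4.1 gives 89% power for recurrence-free rates of 0.600 (sham, n=40) and 0.880 (insert, n=80), two-sided alpha 0.05, continuity-corrected chi-square.
- Pooled rate = (40×0.600 + 80×0.880)/120 = 0.7867.
- Null SE = √[0.7867×0.2133×(1/40+1/80)] = 0.0793. Alternative SE = √[0.6×0.4/40 + 0.88×0.12/80] = 0.0856.
- Continuity term = ½(1/40+1/80) = 0.01875.
- Power = Φ[(0.28 − 0.01875 − 1.96×0.0793)/0.0856] = Φ(1.236) = 0.892. The 89% is reproduced.

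**2. What each rule can reach.**

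| Step | Month 6 | Months 12 and 36 |
|---|---|---|
| Deviation review (SAP 4.3.2) | before unmasking | unmasked, as stated |
| Major list for PP (SAP 5.2) | before lock | before each lock |
| Drug list (SAP 8.1.2) | before lock, study team masked under 4.2.1 | before each lock, masking not stated |
| Staff still masked (SAP 4.2.1) | all but the randomization team | CRO Clinical and Data Management |

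**3. How many calls would matter.** The documents give planned rates for Month 6 only and no imputation rate, so every table here is assumed. The test is X² = N(|ad−bc| − N/2)² / (product of the four margins), where a and c are the recurrence-free counts and b and d the recurrences, insert then sham.

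PP sets are taken after removal of imputed endpoints, assumed to be 10% (80→72, 40→36) or 20% (80→64, 40→32). Example: 63/72 v 22/36 gives ad−bc = 63×14 − 9×22 = 684, and X² = 108×(684−54)²/(72×36×85×23) = 8.46, p=0.0036.

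| Assumed start (insert v sham) | p | After excluding recurring subjects | p |
|---|---|---|---|
| 63/72 v 22/36, near planned | 0.0036 | four sham (22/32); five sham (22/31) | 0.045; 0.081 |
| 56/64 v 19/32, near planned | 0.0040 | three sham (19/29); four sham (19/28) | 0.028; 0.052 |
| 57/72 v 22/36, borderline | 0.078 | one insert (57/71); two insert (57/70) | 0.058; 0.042 |
| 51/64 v 19/32, borderline | 0.062 | one insert (51/63) | 0.044 |

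Excluding recurring sham subjects works against the insert; excluding recurring insert subjects works for it.

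**4. Drug list in the ITT set.** Only users with no earlier recurrence and complete examinations count. Suppose that with one drug listed the table is 63/80 v 24/40, p=0.051. If the drug is not listed:
- 2 insert users and 1 sham user: 65/80 v 25/40, p=0.044.
- 1 and 1: 64/80 v 25/40, p=0.065.
- 0 and 1: 63/80 v 25/40, p=0.093.

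The direction depends on how use divides between the arms. At the planned rates (0.88×80 ≈ 70, so 70/80 v 24/40, p=0.0013), one such sham user gives 70/80 v 25/40, p=0.003.

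**The case against.** The case against giving this weight is substantial.

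- *No confirmatory result is touched.* The Month 6 deviation review precedes unmasking, PP is a supplement to ITT, and the later tests carry no error control. This stands. A reader might infer that the primary result is compromised; SAP 4.2.1 and 4.3.2 do not support that.
- *The unmasked review is disclosed with its reason.* This stands: it is a design weakness, not a contradiction. Nor do the documents show that anyone classified with the arm in mind. They show an opportunity.
- *The drug-list half rests on silence.* This stands. A reader might infer that SAP 8.1.2 reopens the list unmasked. It does not say so; that unmasked staff could do it is an inference from 4.2.1. New drug terms accrue, so identifying the list before each lock is expected. The latitude is also narrow. Only drugs prohibited under protocol 9.10.2 qualify, the list is set by drug term for both arms, and systemic tapers are out. So are topical steroids: "For the analysis of the primary endpoint for US/FDA, topical steroids will not be considered a prohibited medication". Removing a drug already on the Month 6 list would visibly contradict the earlier treatment, so the realistic case is a drug first seen later.
- *SAP 5.2 already has a rules document.* This is a partial safeguard. Its content is not in the documents reviewed, the sponsor may add to it, and whether a deviation is major is a separate decision.
- *The reversals are chosen near the threshold.* This stands. The changes on one or two calls start from p-values between 0.051 and 0.078.
- *Some deviations reveal the arm*, for instance a misplaced insert (protocol 9.7.3) or treatment received that differs from randomization. This also stands, and the fix has to provide for it.

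**Conclusion.** The point holds, as an improvement to consider and not as an error. The stated half is firm: deviations that decide PP membership at Months 12 and 36 are reviewed and identified unmasked, while the plan keeps CRO staff masked who could classify most of them. The drug-list half is a request for clarification.

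The exposure covers the Month 12 and 36 PP analyses and, only if drugs first seen later are classified by unmasked staff, the Month 12 and 36 ITT recurrence tests. It is small if results resemble the planned rates: in the assumed PP tables, nominal significance is lost only after four or five exclusions, all of recurring sham subjects. It is material only for a borderline result. These sizes rest on assumed counts, with Month 6 planning rates carried to later time points and an assumed 10% or 20% of imputed endpoints.

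**What to change.** Four coordinated SAP edits:

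1. **4.3.2.** Replace the sentence on unmasked review with: *Deviations at Months 12 and 36 will be classified by the major-deviation rules (types) fixed before the Month 6 unmasking. Individual occurrences of types not covered will be classified by CRO Clinical and Data Management staff masked to subject-level treatment. Deviations whose nature reveals the arm will be classified by the pre-fixed rules where these apply, and otherwise listed and flagged.*
2. **5.2.** Make it agree. After Month 6, occurrences are still identified before each lock, but the rules for what is major are carried forward, and only masked staff add new ones. Without this edit, 5.2 would conflict with the new 4.3.2.
3. **8.1.2.** Carry the Month 6 drug list forward unchanged, and have drug terms first seen later classified by the same masked staff.
4. **11.2.** Record the changes.

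The cost is SAP text only: no protocol amendment, no new data, no new staff and no change to the Month 6 PP set. The downside is that the sponsor and the unmasked statisticians can no longer refine the lists, and the change is on record as made after unmasking.
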